9.3 Variables

The physician collects historical study-relevant data (demographic and clinical characteristics) from medical records if available (or by interviewing the patient at the initial [baseline] visit) and treatment-related data during visits (see section 9.2.5). In this non-interventional study, the visits are not scheduled by the study team (i.e. visits occur at the physicians' discretion and independent of the

⁶ Events up to 30 days after the last dose of damoctocog alfa pegol within the study period.

⁷ Including duration, treatment, seriousness and outcome.

⁸ Sodium, potassium, albumin, creatinine, bilirubin, aspartate aminotransferase (AST), alanine aminotransferase (ALT), gamma-glutamyl transferase (GGT), alkaline phosphatase, C-reactive protein (CRP), urea, estimated glomerular filtration rate (eGFR).

⁹ Urine albumin/creatinine ratio, spot urine dipstick test.

¹⁰ Including (for all ages) level of consciousness, cranial nerves, body tone, strength (of the four extremities), reflexes, sensory aspects, gait and coordination and fine motor function. In the case of children, evaluation of appearance, language, social interaction. In the case of adults, mental state.

patients' participation in the study. It is assumed that at most Hemophilia treatment centers; patient visit frequency is at least 1-2 times per year). The physician documents the study-relevant data for each patient in the eCRF/EDC system. The pCRF (paper version of the eCRF) is kept as a stand-alone document (see [Table 3](#)) and is available upon request.

This is a non-interventional study and the clinical decisions of the physicians must not be affected by study participation. As such, data on many of the secondary endpoints (e.g. PEG-plasma, eGFR, ALT) may not be available for all patients. Nevertheless, if they were collected in local routine clinical practice at the investigator's discretion, all results will be documented in the eCRF/EDC system. In the case that an investigator wants to determine the PEG levels in plasma, e.g. in case of any AE which could be related to PEG accumulation, one or more laboratories will be appointed and kits will be provided to the sites for sampling as per the investigator's discretion. Bayer Consumer Care AG will offer support for the procedure if requested.

All variables that are available should be recorded by physicians (in the eCRF/EDC); the importance of obtaining complete data (as complete as possible given the non-interventional nature of the study) will be highlighted to the physicians when they are trained prior to study start.

A detailed list of variables collected in this study is kept as a stand-alone document and is available upon request ([Table 3](#))

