9.1 Study design

This is a multinational, open-label, prospective, non-interventional, multicenter, cohort study of PTPs with hemophilia A receiving damoctocog alfa pegol as prophylaxis treatment. The study is planned to be conducted in multiple countries in Europe.

At study start, retrospective data will be collected on the patients' baseline characteristics (including genotyping [where available], medical condition and hemophilia treatment history). Also at study start and then at each physician visit during the follow-up phase, data will be recorded on regimens used, AEs of special interest including hypersensitivity reactions, loss of drug effect, renal impairment, neurocognitive disorders, inhibitor development, other AEs, SAEs and drug-related ARs in standard clinical practice. If collected in routine clinical practice at the physician's discretion, parameters relating to kidney and liver function (e.g. creatinine, estimated glomerular filtration rate (eGFR), alanine transaminase (ALT), aspartate aminotransferase (AST), bilirubin), PEG-plasma level and abnormal findings from neurological assessments will be captured in the eCRF/EDC system. Adverse reactions (ARs) relating to the system organ classes of the nervous system and psychiatric disorders will be recorded.

Patients/legal representatives and physicians can choose from different prophylaxis regimens with damoctocog alfa pegol following approved local labels or any other regimen prescribed by the physician as part of normal clinical practice. Patients/legal representatives and physicians can choose to change the dosing regimen based on the patient's response to treatment at any time. A reason for the dose and/or frequency change should be documented.

The planned observation period for each of at least 50 patients will be a minimum of 48 months for the collection of long-term safety data and the prospective monitoring of clinical effects of long-term exposure of prophylaxis with damoctocog alfa pegol in PTPs with hemophilia A.

Due to the observational nature of the study, follow-up visits cannot be scheduled specifically for study purposes and it is unknown when a patient will come for the next visit. Thus, data collection will occur continuously throughout the patient's observational period (i.e., each visit or assessment

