9.1.2 Secondary endpoints

The secondary endpoints are:

- Number of ARs that are defined within the system organ classes nervous system and psychiatric disorders from study start to end of the study
- Number of ARs related to hepatic or renal function from study start to the end of the study
- Change in kidney and liver function parameters from study start to the end of the study
- Change in PEG-plasma levels from study start to the end of the study
- Number of patients with abnormal findings as assessed by neurological examination across all age groups from study start to the end of the study

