9.5 Study size

The study aims to observe 50 patients for at least 4 years each, in line with the sample size, requested the safety analysis by the Authority (EMA). Assuming a dropout rate of approximately

20% (due to lost to follow-up cases or withdrawals), 60 patients will be enrolled. The study will continue until 50 patients have reached a minimum follow-up of 4 years. At this time, the study will end for all patients.

With an underlying incidence risk of 2%, there is a 64% chance of observing at least one event in a sample of 50 patients.

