9.7 Data analysis

9.7.1 Statistical considerations

Statistical analyses will be of an explorative and descriptive nature. The study is not aimed to confirm or reject predefined hypotheses; hence no formal hypothesis testing will be performed.

All variables will be analyzed descriptively with appropriate statistical methods: categorical variables by frequency tables (absolute and relative frequencies) and continuous variables by sample statistics (i.e., mean, standard deviation [SD], minimum, median, quartiles, and maximum). Continuous variables will be described by absolute value and as change from baseline per analysis time point, if applicable.

All analyses will be performed for the total study population (overall analysis).

Sample size and disposition information including reasons for discontinuation by analysis time point will be displayed in a frequency table.

All therapies documented in the following forms will be coded using the World Health Organization Drug Global.

- Prior and concomitant medication

Any diagnoses/diseases/event terms documented in the following forms will be coded using the latest Medical Dictionary for Regulatory Activities (MedDRA) version:

- General medical/surgical history
- Adverse events

Interim reports will be provided annually to the competent authorities as specified in the milestones. The final analysis will be performed after the end of the study, which is the date the analytical dataset is completely available.

All statistical details including calculated variables and proposed format and content of tables will be detailed in the Statistical Analysis Plan (SAP). Bayer Consumer Care AG will provide oversight of data analysis activities that will be assigned to a CRO. All specific processes and technical details will be documented by the CRO statistician in the SAP and tables specification manual. The SAP will be finalized before the first database lock. The SAP will be available upon request (see [Table 3](#)).

Analysis populations:

The Safety Analysis Set (SAF) include all patients who took at least 1 dose of damoctocog alfa pegol in the study

Missing data:

Because the aim of this study is to obtain data under conditions of routine clinical care (i.e., naturalistic settings), some patients may have missing values for some variables. To address missing data, the following strategy will be applied:

- In general, clinical outcomes collected in the study will not be imputed.

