9.7.4 Analysis of secondary variables

Laboratory parameters will be analyzed descriptively. Results will be displayed by summary statistics and as change from baseline.

A descriptive analysis will be performed for the number of patients with laboratory parameters outside of the normal ranges.

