9.9 Limitations of the research methods

In general, because of the non-interventional study design and limitations inherent to observational studies, findings generated from this study are subject to bias, such as information bias, selection bias, limitations to availability of historical medical data, and differences in treatment or reporting owing to local guidelines. Furthermore, due to the study being non-interventional, the information to be collected is limited to and depending on the visits/assessments occurred in routine clinical practice. Therefore, it cannot be forced that complete data on hepatic and renal function and neurological assessments will be available for final analyses as the performance of these assessments is highly depending on the physician's discretion. Nevertheless, any clinically relevant change in organ functions or development of new symptoms would be documented as AE and would trigger lab assessments in routine clinical practice.

The sample size is not large enough to observe rare AEs. Furthermore, if a rare AE is observed, the sample size is not large enough to draw any conclusions on the association. It may include limited availability of treatment data and underreporting of safety outcomes if a patient leaves the study and/or is not possible to be followed-up adequately (e.g., withdrawal of consent or loss to follow-up).

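### PEG and organ-function values are taken at discretion and partly because of an event, yet are summarised as cohort change; section 9.1 also limits neurological capture to abnormal findings

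*Protocol*

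**What the plan says.** **Endpoints and analysis.** Section 9.1.2 lists "Change in PEG-plasma levels from study start to the end of the study", the matching change in kidney and liver parameters, and the number of patients with abnormal neurological findings over the study. For laboratory parameters, section 9.7.4 says "Results will be displayed by summary statistics and as change from baseline" and adds a count of patients outside normal ranges.

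**How values arise.** Biochemistry, urinalysis, PEG and neurological results are recorded only if available from routine care (sections 9.1 and 9.3.2; Table 2, footnote 5). Section 10.1 requires no extra monitoring. Section 9.3 arranges laboratories and kits for an investigator who wants a PEG level, for example "in case of any AE which could be related to PEG accumulation". Section 9.9 says a clinically relevant organ change or new symptom would be recorded as an AE and "would trigger lab assessments in routine clinical practice".

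**Neurological capture.** Section 9.1 says "abnormal findings from neurological assessments will be captured in the eCRF/EDC system". Section 9.3, on secondary-endpoint data obtained in routine practice, says "all results will be documented in the eCRF/EDC system". Section 9.3.2 lists a dated assessment covering every domain. Section 9.8.2 checks that sites know all available neurological data must be collected.

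**Inhibitors.** Follow-up testing is optional (section 9.3.1). A negative test before entry is required (section 9.2.1.1). Incidence risks and exposure-adjusted rates use the SAF and treated person-time (sections 9.7.1 and 9.7.3).

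**The concern.** A mean change describes the cohort only if having a value is unrelated to what the value would be. Here the protocol itself describes two routes by which a suspicious event leads to a measurement: PEG sampling after a suggestive AE, and laboratory tests after an organ change. Section 9.9 offers the second as reassurance about completeness, but it is also outcome-dependent measurement. PEG is the most exposed: no baseline sample is assured, and a possible accumulation event is the only sampling occasion named. A reader looking for a PEG or renal signal could see a shift that comes from selection.

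The neurological problem is one of capture. If only abnormal findings are entered, an examined patient with normal findings looks the same as a patient never examined. The number examined is then unknown, and an abnormality cannot be called new because no normal baseline was stored. An SAP cannot recover data that were not entered.

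**Working it through.** **1. The plan's own figure.** Section 9.5 states: "With an underlying incidence risk of 2%, there is a 64% chance of observing at least one event in a sample of 50 patients". Check: 1 − 0.98^50 = 0.636, so it reproduces. It assumes that all 50 patients are ascertained. Section 9.7.1 says "hence no formal hypothesis testing will be performed", so there is no power calculation to check.

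**2. How selection moves a mean (all inputs assumed; the protocol gives no testing rates).** Let a fraction p of patients have a value raised by D, with the rest unshifted. Let a be the probability that a raised patient is tested and b the probability for the others.

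- True cohort mean = D·p
- Fraction tested T = p·a + (1 − p)·b
- Mean among those tested = D·p·a / T

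With D = 2 SD, p = 0.10 and a = 0.80, the true mean is 0.20 SD and D·p·a = 0.16:

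| b | T | Mean among tested |
|---|---|---|
| 0.80 | 0.08 + 0.72 = 0.80 | 0.20 SD |
| 0.50 | 0.08 + 0.45 = 0.53 | 0.30 SD |
| 0.20 | 0.08 + 0.18 = 0.26 | 0.62 SD |
| 0.05 | 0.08 + 0.045 = 0.125 | 1.28 SD |

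There is no distortion when testing is unrelated to outcome, and it grows as testing becomes event-driven.

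**3. Does separating routine from triggered values help?** If routine tests occur at the same rate b in both groups, the routine-only mean is D·p·b / [p·b + (1 − p)·b] = D·p = 0.20 SD, which is correct. If raised patients are tested only because of events, the routine-only mean is 0. So the triggered values must be shown as well, not discarded.

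**4. Inhibitor denominators.** Assume a true risk of 2%, every case tested and half of non-cases tested. The SAF figure is 2.0%. The tested-only figure is 0.02 / (0.02 + 0.98 × 0.5) = 0.02 / 0.51 = 3.9%. If instead testing is independent of inhibitor status and untested inhibitors never surface, 25 of 50 tested turns 2% into 0.02 × 0.5 = 1.0% on the SAF, and the chance of seeing at least one event falls from 64% to 1 − 0.98^25 = 40%. The document does not say which case applies, so the number tested is needed to read either figure.

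**5. Neurological wording side by side.** Section 9.1: abnormal findings. Section 9.3: all results. Section 9.3.2: date plus every domain. Section 9.8.2: all available data. Section 9.2.5: each visit or assessment documented. Section 9.1 stands alone against the rest. The section 9.1.2 count has no rule separating new from existing findings. The domains include gait and strength, and section 7.1 describes joint damage and lost mobility in this disease, so findings present at entry are plausible, although 7.1 does not itself describe neurological abnormality.

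**The case against.** The PEG sentence in section 9.3 is mainly about supplying kits, and the AE is only an example; discretionary routine sampling is equally allowed. That stands: event-triggered testing is documented only for PEG, as an example, and for organ-function tests. A reader might extend it to inhibitor and neurological testing, but the protocol does not say so.

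Section 9.7.4 does not say that triggered and routine values go into one mean, and it fixes no denominator for laboratory or neurological counts. Handling of unscheduled values, denominators and shift tables is normal SAP content. The detailed variable list and paper CRF are stand-alone documents and may already hold the reason for a test. All of this stands, so no pooling error or wrong denominator is shown for those counts.

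A reader might infer that inhibitor incidence is biased low because untested patients count as event-free. That needs testing to be independent of having an inhibitor and untested inhibitors never to surface, whereas loss of drug effect is itself an AE of special interest with a follow-up questionnaire. The inhibitor baseline is also sound, since entry requires a negative test. Replacing the SAF denominator with tested patients would inflate risk under event-driven testing (3.9% against 2%).

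The protocol does disclose incompleteness and general information bias, promises to report the extent of missing data, trains sites, and is descriptive only. But incompleteness is not the same as testing that depends on outcome, and reporting its extent does not remove the distortion.

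The neurological phrase may be loose drafting, since most other sections say otherwise. It is still an instruction about what enters the database.

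**Conclusion.** The point holds in a limited form. For PEG and kidney and liver values, the protocol describes discretionary and partly event-driven measurement, defines the endpoints as cohort change, and does not acknowledge that the means may depend on who was tested because of an event. The size, and whether it matters in practice, cannot be computed from the document; the 0.20 to 1.28 SD range is an illustration resting on assumed prevalence, shift and testing rates.

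For neurology there is a plain contradiction between section 9.1 and sections 9.3, 9.3.2 and 9.8.2. If section 9.1 is followed, the loss is permanent: no number examined, no normal baseline, and no way to tell new from pre-existing findings in the section 9.1.2 count.

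The document does not support a claim that inhibitor incidence is biased low, or that its SAF and treated person-time denominators are wrong. This is worth correcting during data collection, because the reason for a test and unrecorded normal examinations cannot be reliably rebuilt years later.

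**What to change.** - Correct section 9.1 so that every neurological assessment performed is recorded, normal or abnormal.
- If the eCRF does not already do so, record for each PEG and laboratory result whether it was routine or event-triggered, and for PEG the time of the last infusion (section 7.2 refers to a peak level, so timing affects interpretation).
- Base change-from-baseline summaries on paired routine values, and list triggered values separately beside them, since neither display alone describes the whole cohort.
- Count laboratory and neurological abnormalities as new or worsened where a baseline exists.
- Keep the SAF and treated person-time for inhibitor incidence. Report the number of patients with at least one post-baseline inhibitor test; any tested-only figure is a supplement.
- State in section 9.9 that testing may depend on outcome.

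Cost: one or two eCRF fields, entry of normal neurological results, some SAP wording, and smaller numbers in the change tables. No test or visit is added, so the study stays non-interventional.

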9.3.1 Variables to determine the primary endpoint

(Serious) adverse events need to be collected as described in section [11.2](#). Information to be collected includes:

- Diagnosis of AE or symptom (if diagnosis unknown).
- Qualification as AE of special interest including hypersensitivity reactions, loss of drug effect, renal impairment, neurocognitive disorders, and inhibitor development.
- Start and stop date.
- Seriousness.
- Reasonable causal relationship to damoctocog alfa pegol treatment.
- Action taken.
- Event outcome.
- Other specific treatment(s) of AE.

Information to be documented by the physician regarding inhibitor measurement, if available and collected in routine clinical practice, includes:

- Date of inhibitor measurement.
- Inhibitor result (no/yes).
- Titer of inhibitor (Bethesda units).

9.3.2 Variables to determine the secondary endpoints

The main variables for determination of the secondary endpoints comprise variables to be collected on laboratory tests:

Laboratory parameters to be documented include (if available and collected in routine clinical practice at the physician's discretion):

- Date of test
- Biochemistry parameters:
 - Sodium, potassium, albumin, creatinine, bilirubin, aspartate aminotransferase (AST), alanine aminotransferase (ALT), gamma-glutamyl transferase (GGT), alkaline phosphatase, C-reactive protein (CRP), urea, estimated glomerular filtration rate (eGFR).
- Urinalysis parameters:
 - Urine albumin/creatinine ratio and spot urine dipstick test.
- PEG plasma levels

Parameters for neurological assessments to be documented if available include the following:

- Date of assessment
- Level of consciousness, cranial nerves, body tone, strength (of the four extremities), reflexes, sensory aspects, gait, coordination and fine motor function, mental state.
- For children: evaluation of appearance, language, social interaction.

9.4 Data sources

The physician collects historical study-relevant data (demographic and clinical characteristics) from medical records, if available, or else by interviewing the patient. Likewise, the physician collects treatment-related data during visits that take place in routine practice. Patient diaries will be provided to the patients and they will be trained by the site personnel on how to complete them. Patient diaries will be reviewed for AEs at each visit.

Each patient is identified by a unique central patient identification code, which is only used for study purposes. For the duration of the study and afterwards, only the patient's treating physician or authorized site personnel are able to identify the patient based on the patient identification code.

In case a patient is seen by more than one physician (e.g., the patient is monitored by a physician other than the initial treating physician), the initial treating physician should make every effort to collect information on any visits (including results) that have taken place outside the treating physician's site for example by communicating with the other physician or by having the patient/legal representative obtain a letter with detailed information and results, for example of any ARs, medications given, or procedures performed.

9.5 Study size

The study aims to observe 50 patients for at least 4 years each, in line with the sample size, requested the safety analysis by the Authority (EMA). Assuming a dropout rate of approximately

20% (due to lost to follow-up cases or withdrawals), 60 patients will be enrolled. The study will continue until 50 patients have reached a minimum follow-up of 4 years. At this time, the study will end for all patients.

With an underlying incidence risk of 2%, there is a 64% chance of observing at least one event in a sample of 50 patients.

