	
The variables for the secondary objective are:
 
Laboratory parameters (including date of test), if collected in routine clinical practice at the physician’s discretion:
 
 • Biochemistry parameters: 
 ○ Sodium, potassium, albumin, creatinine, bilirubin, aspartate aminotransferase (AST), alanine aminotransferase (ALT), gamma-glutamyl transferase (GGT), alkaline phosphatase, C-reactive protein (CRP), urea, estimated glomerular filtration rate (eGFR). • Urinalysis parameters: 
 ○ Urine albumin/creatinine ratio and spot urine dipstick test. • PEG plasma levels 
Parameters for neurological assessments to be documented if available include the following:
 
 • Date of assessment • Level of consciousness, cranial nerves, body tone, strength (of the four extremities), reflexes, sensory aspects, gait, coordination and fine motor function, mental state. • For children: evaluation of appearance, language, social interaction.

Data sources
	
Historical data based on medical records or on information provided by the patient during routine clinical visits. Treatment-related data documented during visits that take place in routine practice.

Study size
	
The study aims to observe 50 patients for at least 4 years each. Assuming a dropout rate of approximately 20% (due to lost to follow-up cases or withdrawals), 60 patients will be enrolled.

Data analysis
	
Statistical analyses will be of an explorative and descriptive nature. The study is not aimed to confirm or reject predefined hypotheses; hence no formal hypothesis testing will be performed.
 
All variables will be analyzed descriptively with appropriate statistical methods: categorical variables by frequency tables (absolute and relative frequencies) and continuous variables by sample statistics (i.e., mean, standard deviation [SD], minimum, median, quartiles, and maximum). Continuous

	variables will be described by absolute value and as change from baseline per analysis time point, if applicable.
Milestones	First patient first visit: Q2 2020 Last patient first visit: planned Q2 2023 Last patient last visit: planned Q2 2028 Final report: planned Q4 2028

5. Amendments

None.

6. Milestones

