9.2.3 Replacement

Enrollment will stop as outlined in the milestones or when the target sample size is reached. Patients who drop out after the end of enrollment (e.g. withdrawal, lost to follow-up) will be replaced to ensure that all in all 50 patients have reached a minimum follow-up of 4 years.

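### At the stated dropout of about 20%, enrolling 60 patients yields an expected 48 with four years of follow-up, not 50, because the allowance was added to 50 rather than divided out (minor)

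*Protocol*

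**What the plan says.** **Target.** Protocol Section 9.5 reads "The study aims to observe 50 patients for at least 4 years each, in line with the sample size", and attributes that number to the regulator's request. Section 7.2 ties it to a post-approval commitment.

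**Dropout allowance.** The Section 4 abstract gives it in full: "Assuming a dropout rate of approximately 20% (due to lost to follow-up cases or withdrawals), 60 patients will be enrolled". Section 9.5 repeats it in the same terms: "20% (due to lost to follow-up cases or withdrawals), 60 patients will be enrolled".

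**End of study.** Section 9.5: "The study will continue until 50 patients have reached a minimum follow-up of 4 years". Sections 9.1 and 9.2.5 agree. The end depends on that count, not on a date.

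**Enrolment stop and replacement.** Section 9.2.3: "Enrollment will stop as outlined in the milestones or when the target sample size is reached". It continues: "Patients who drop out after the end of enrollment (e.g. withdrawal, lost to follow-up) will be replaced", with the stated purpose that 50 patients in all reach four years.

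**Dates.** The abstract plans the first patient's first visit for Q2 2020 and the last patient's first visit for Q2 2023. It then gives "Last patient last visit: planned Q2 2028". Section 6 lets milestones change without amendment, but names only delays in study preparation and enrolment as reasons.

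**The concern.** A dropout allowance has to be divided out of the target. If a fraction d is lost, N enrolled leaves N(1 - d), so N must be target / (1 - d). Multiplying the target by (1 + d) gives too few patients, and the stated 60 is exactly what that multiplication produces.

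In many descriptive studies a gap of two patients would be cosmetic. Here the count of 50 is both the number the regulator asked for and the event that ends the study. A plan whose own dropout figure leads to 48 should say so, or enrol enough to reach 50. The replacement rule is the only mechanism that closes the gap, so what it covers, and by when, also matters.

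**Working it through.** **Inputs.** Target 50, dropout d = 0.20 and enrolment 60 (Sections 4 and 9.5). First patient first visit Q2 2020, last patient first visit Q2 2023, last patient last visit Q2 2028 (Section 4, Milestones). Follow-up of 48 months (Section 9.1).

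**1. Where 60 comes from.**
- 50 x (1 + 0.20) = 60, which reproduces the stated figure.
- 50 / (1 - 0.20) = 62.5, rounded up to 63, which does not.

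**2. What 60 delivers.**
- At 20% dropout: 60 x 0.80 = 48, two short of 50.
- Dropout at which 60 leaves exactly 50: 1 - 50/60 = 16.7%.
- With 63 enrolled at 20%: 63 x 0.80 = 50.4.

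**3. Chance that at least 50 complete, before any replacement.** The number completing is taken as binomial (N, 1 - d), with patients independent.

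| Enrolled | Dropout | Expected completers | P(at least 50) |
|---|---|---|---|
| 60 | 15% | 51.0 | 72% |
| 60 | 16.7% | 50.0 | 58% |
| 60 | 20% | 48.0 | 32% |
| 63 | 20% | 50.4 | 62% |

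**4. Which replacements can finish on schedule.** Q2 2028 less 48 months is Q2 2024. Enrolment is planned to close in Q2 2023, so replacements have a one-year window in which they can still reach four years by the planned last visit.

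**5. How dropouts fall against that window.** The protocol gives no accrual pattern or dropout timing. As an illustration, assume uniform entry from Q2 2020 to Q2 2023 and a constant dropout hazard giving 20% at four years. The expected 60 x 0.20 = 12 dropouts then split as follows:
- about 40% (4.8 patients) before enrolment closes, which the wording of the replacement sentence does not cover;
- about 25% (3.0 patients) from Q2 2023 to Q2 2024, replaceable on schedule;
- about 35% (4.3 patients) after Q2 2024, replaceable only if the last visit moves.

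**6. What the rule adds by Q2 2028.** Under the same assumptions, with each dropout in the one-year window replaced at once and 20% dropout among replacements, the expected number is 48 + 3.0 x 0.80 = 50.4, and P(at least 50) is 64% by simulation. If each replacement takes time to enrol:

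| Lag to replacement | Expected four-year patients by Q2 2028 | P(at least 50) |
|---|---|---|
| none | 50.4 | 64% |
| 3 months | 49.8 | 56% |
| 6 months | 49.2 | 48% |
| 12 months | 48.0 | 32% |

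**The case against.** The best defence is that the plan does not rely on 60 alone. It replaces dropouts, and it continues until 50 patients have four years. With immediate replacement, the illustration in step 6 gives much the same result as enrolling 63 without replacement (50.4 expected in both cases; 64% against 62%). That stands, and it is why the 32% must be read as a figure before replacement. The benefit does shrink as the lag grows, and it is gone at 12 months.

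The dropout figure is also only approximate, and 60 does suffice at 16.7%. But the protocol writes 20% and gives no other basis for 60, so the stated numbers remain inconsistent.

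Little in the analysis depends on two patients. The study is descriptive with no hypothesis test (Section 9.7.1). The safety set takes everyone with at least one dose, and rates use time on prophylaxis, so dropouts still contribute. The chance of seeing at least one event at a 2% risk is 1 - 0.98^50 = 63.6% (the protocol's 64%), against 1 - 0.98^48 = 62.1%. This stands, and it limits the severity.

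Two stronger readings are tempting, and the document supports neither. A reader might infer that replacement cannot produce four-year patients by the planned last visit. The planned dates leave five years between last first visit and last visit, so replacements entering by Q2 2024 can finish on time. A reader might also infer that the study could never meet its end rule. That rule depends on a count, so a shortfall mainly delays the last visit. Section 6 names only preparation and enrolment delays, so whether it covers a delay from late replacement without an amendment is arguable.

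**Conclusion.** The sample-size arithmetic in Sections 4 and 9.5 is wrong. At the stated dropout, 60 enrolled gives an expected 48 four-year patients and a 32% chance of at least 50 before replacement; 63 is the number consistent with 50 and 20%. This part needs only the protocol's figures, plus independence between patients for the probability.

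Section 9.2.3 is incomplete in two lesser respects: it does not mention patients lost while enrolment is still open, and it does not say what happens to the planned last visit when a replacement enters after Q2 2024. How many patients this affects rests on the assumed entry and dropout pattern; the Q2 2024 date follows from the milestones alone.

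The consequence is a small shortfall at the planned date or a later study end. Severity is minor.

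**What to change.** **Sections 4 and 9.5.** Choose one:
- keep 60, and state that it tolerates about 17% dropout and yields about 48 four-year patients at 20% before replacement; or
- state 63 enrolled, from 50 / 0.80.

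**Section 9.2.3.** Extend replacement to patients who drop out during enrolment. State that a replacement entering after Q2 2024 cannot reach 48 months by Q2 2028, and that the last visit moves beyond that date if such replacements are needed to reach 50.

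A fixed calendar end is not advised as part of this change. It would let the study close with fewer than 50 four-year patients, which the present end rule prevents.

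**Cost.** Wording in three places, plus either a less favourable stated yield (48 before replacement) or three more patients. No analysis changes.
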